#### Appendix F - Definition of the composite endpoint

1: Stroke is defined as rapid onset of a focal/global neurological deficit, with duration ≥ 24 hours, or resulting in death, or supported by clear evidence of cerebral infarction on diffusion-weighted MRI imaging. There must be no other readily identifiable non-stroke cause for the clinical presentation.

Stroke is sub-categorized as follows:

- -1a: Ischemic stroke, defined as stroke caused by lack of blood supply (e.g. thrombosis, embolism, systemic hypoperfusion or cerebral venous sinus thrombosis)
- -1b: Hemorrhagic stroke, defined as a stroke caused by cerebral or subarachnoid hemorrhage.
- -1c: Unspecified stroke, in case the patient did not undergo brain imaging or autopsy
- 2: Systemic arterial embolism include arterial embolic events that do not reach the brain; these may reach organs such as kidney, spleen, heart, intestine, eyes and extremities.

Adjudication is based on clinical evaluation of patient data.

Transient ischemic attack (TIA) is not a primary event, and is defined as a transient episode of neurologic dysfunction caused by focal brain, spinal cord, or retinal ischemia, **without** acute infarction.

Explanation: TIA was originally defined clinically by the temporary nature (<24 hours) of the associated neurologic symptoms. However, the arbitrary nature of the 24-hour time limit and lack of specific pathophysiologic meaning hampered the clinical and research utility of the term "TIA." Recognition of these problems led to a change to a tissue-based definition of TIA. The change was driven by advances in neuroimaging that enabled very early identification of ischemic brain injury and endorsed by 2009 guidelines from the American Heart Association and American Stroke Association (AHA/ASA).

#### Appendix G -Funding

Research grants have been obtained from the Danish National Foundation for Strategic Research (DKK 15.6 mio), the Research Foundation for the Capital Region of Denmark (DKK 2.0 mio) and the Danish Heart Foundation (DKK 150.000).

The first 600 implantable loop recorders(ILRs) used in the project will be purchased from the study funding from the Danish National Foundation for Strategic Research. The condition of this purchase has been altered so that the Reveal LINQ's will be offered on the same terms as the original Reveal XT devices. The additional 900 Reveal LINQ ILRs will be donated from Medtronic as an unrestricted research grant (which has a value of DKK 5.4 mio (reduced price) or DKK 22.5 mio (ordinary list price)) and a grant to cover salary for research nurses at the hospitals (DKK 1.9 mio).

Medtronic has decided to support the LOOP study with an unrestricted research grant covering salaries for one research nurse for one year at each of the four participating hospitals (i.e. a total of four years of salary for research nurses; estimated salary per nurse including pension and vacation is 40,000 DKK per month which equals 480,000 DKK per year/nurse; i.e. a total of 1.920.000 DKK (the same salary estimate was used in the application to the Strategic Research Council).

Additional research grants will be applied for from private and public research foundations as well as from industry. Study participants and the Ethics committee will be informed about additional funding. Patients will not receive compensation for their participation in the study, but may in selected cases receive compensation for their transport expenses.

# 1 Purpose

The committee will provide standardized adjudication of relevant protocol-defined events for the LOOP study. Events will include trial endpoints (excluding Quality of Life) and important specific adverse events. This charter describes the roles and responsibilities of the committee for adjudication of the primary endpoints. All members of the committee will adjudicate all endpoints that potentially could be a primary endpoint.

#### 2 Roles of CEC Members

The primary roles of CEC members will be:

- 1. To review and provide input for this Charter;
- 2. To adjudicate all reported events as per this Charter;
- 3. To classify all endpoints into their specific type according to the set of definitions in this document.

Processes for adjudication and definitions for the events that will be adjudicated by the committee are described in this Charter. The committee will review and adjudicate all strokes and systemic embolisms and all deaths. The committee can include additional expertise as required for evaluation of events, and may obtain assistance in assessment of events.

# 3. Reporting events to the Committee

Potential endpoints will be reported in the eCRF, and supporting documentation (e.g., admission summaries, progress records, diagnostic test reports, consultant evaluations, discharge summaries, death certificates, autopsy reports) will be forwarded by each center to the Study Office at Rigshospitalet. The study administrator will gather all relevant material in patient specific binders, which will be used by the CEC. The study administrator will interact with study sites to collect additional documentation needed to prepare a complete document package for committee adjudication.

# 4. Documentation for CEC adjudication

Supporting documentation required for adjudication of an event may include but is not limited to the following:

- Emergency Department records
- Pertinent laboratory reports
- Selected reports from any other test performed to evaluate the patient
- Hospital admission notes and pertinent hospital record notes surrounding the event (physician notes and nursing notes)
- Selected consultant reports and pathology reports
- Hospital or Emergency Department discharge summaries
- Death/autopsy summary
- Selected relevant hospital records
- Narrative summary of the event

The supporting documentation will have all patient identifiers (name, CPR number and information about randomization) removed or completely obscured prior to submission to the study office and supplied with a study number.

Whenever possible, suspected endpoints will be presented to the CEC only when a complete package of information has been obtained (e.g., all appropriate eCRF information and an adequate set of supporting documentation).

Adjudicators will review the documentation as hard copies.

# 5. Evaluation of the event by the Committee

All cases of potential stroke, TIA or systemic embolism (or death) will be reviewed independently by two CEC members. If the committee members agree on the adjudication, the adjudication is considered complete. If the committee members disagree on adjudication, the event will be reviewed during a CEC meeting. If an event cannot be classified due to a lack of supportive documentation, the CEC will ask for additional information from the study coordinator. After all possible information is gathered, the CEC will render a final adjudication on the event. In certain death cases, only limited medical information may be available. CEC members should use their best clinical judgment when rendering a final decision based on available data and the event definitions within this Charter.

# 6. Reporting of the Committee decision

The completion of the adjudication eCRFs constitutes the committee decision. This decision will not be communicated to the sites before the end of the study.

#### 7. Definition of events for CEC

Events requiring adjudication include:

- Stroke (or TIA)
- Systemic embolism
- Death

Source documentation will be reviewed for determination as to whether the event meets the classification criteria established in this charter. Decisions by the committee will be based on the documentation provided and good clinical judgment.

The CEC adjudication categories for study events are as follows. Further information for each is provided below.

#### ADJUDICATION OF STROKES

Brain imaging is required for all patients with symptoms of stroke or TIA to distinguish hemorrhagic from ischemic stroke.

- 1: Stroke is defined as the sudden onset of a focal neurologic deficit due to acute infarction of cerebrovascular cause lasting at least 24 hours or interrupted by death, and is categorized as follows:
- -1a: Ischemic stroke, defined as stroke caused by lack of blood supply (e.g. thrombosis, embolism, systemic hypoperfusion or cerebral venous sinus thrombosis)
- -1b: Hemorrhagic stroke, defined as a stroke caused by cerebral or subarachnoid hemorrhage.
- -1c: Unspecified stroke, in case the patient did not undergo brain imaging or autopsy *Explanation: Above definitions have been used in the RE-LY, ARISTOTLE and ROCKET AF studies.*
- 2: Transient ischemic attack (TIA) is defined as a transient episode of neurologic dysfunction caused by focal brain, spinal cord, or retinal ischemia, **without** acute infarction.

Explanation: TIA was originally defined clinically by the temporary nature (<24 hours) of the associated neurologic symptoms. However, the arbitrary nature of the 24-hour time limit and lack of specific pathophysiologic meaning hampered the clinical and research utility of the term "TIA." Recognition of these problems led to a change to a tissue-based definition of TIA. The change was driven by advances in neuroimaging that enabled very early identification of ischemic brain injury and endorsed by 2009 guidelines from the American Heart Association and American Stroke Association (AHA/ASA).

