# 7.3 Endpoint Determination:

# 7.3.1 Definition of Endpoints:

Please see Section 10. Details are provided in Appendix F.

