# 10.2 Study Endpoints and Subsets:

# **10.2.1 Primary Endpoint:**

Efficacy (time to at least one of the components of the combined primary endpoint):

- adjudicated stroke or
- adjudicated systemic arterial embolism

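### The protocol defines stroke, the main component of the primary endpoint, in two conflicting ways (Appendix F and the Endpoint Committee Charter) and does not say which governs adjudication

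*Protocol*

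**What the plan says.** Section 10.2.1 makes the primary endpoint the time to an adjudicated stroke or an adjudicated systemic arterial embolism. On what counts as a stroke, Section 7.3.1 refers to Section 10 and adds: "Details are provided in Appendix F".

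Appendix F reads: "Stroke is defined as rapid onset of a focal/global neurological deficit, with duration ≥ 24 hours, or resulting in death, or supported by clear evidence". The evidence meant is infarction on diffusion-weighted MRI. It adds that no other non-stroke cause may be readily identifiable. It lists ischaemic (1a), haemorrhagic (1b) and unspecified (1c) subtypes.

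The Endpoint Committee Charter (Appendix J), under Adjudication of Strokes, reads: "Stroke is defined as the sudden onset of a focal neurologic deficit due to acute infarction of cerebrovascular cause lasting at least 24 hours". A deficit that death cuts short before then also qualifies. It lists the same three subtypes. It defines TIA as a "transient episode of neurologic dysfunction caused by focal brain, spinal cord, or retinal ischemia" and requires that there be no acute infarction.

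The charter's Sections 2 and 7 tell the committee to classify events by the charter's own definitions and criteria. Its Section 5, on deaths with little information, asks for a decision "based on available data and the event definitions within this Charter". Section 7.3.2 and Appendix B also send the reader to the charter. Section 10.7.2, which sets up the blinded committee, refers instead to Appendices B and F.

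**The concern.** An adjudicated endpoint is only as well defined as the text the adjudicators apply. Here two texts in one protocol give different answers for some patients, and each has some claim to govern.

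The number of primary events also helps decide when the trial ends. Section 10.1 ties the end to 279 strokes or to 36 months of follow-up in 6,000 subjects, and Section 10.3 adjusts follow-up to the event count. The choice of definition therefore affects what is estimated, how many events count and when the trial stops. An adjudicator who meets a short deficit with infarction on MRI finds no charter category for it and has to improvise.

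**Working it through.** **1. The two definitions applied to the same patients**

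| Event | Appendix F | Charter |
|---|---|---|
| Focal deficit from infarction, at least 24 h | Stroke | Stroke |
| Focal deficit under 24 h, patient survives, infarction on diffusion-weighted MRI | Stroke | Not stroke (too short); not TIA (infarction present) |
| Global deficit, at least 24 h or fatal | Stroke | Outside the general definition (focal only) |
| Focal deficit from haemorrhage, at least 24 h | Stroke, 1b | General definition says no; subtype 1b says yes |
| Focal deficit at least 24 h, no imaging or autopsy | Stroke, 1c | General definition requires infarction; subtype 1c says yes |

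Rows 2 and 3 are conflicts between the documents. Row 2 turns on "supported by clear evidence of cerebral infarction on diffusion-weighted MRI imaging", which the charter lacks. In Appendix F that criterion fits its TIA definition, because a short deficit with infarction on diffusion-weighted MRI becomes a stroke. The charter keeps the same TIA definition without the criterion, which leaves the gap. Rows 4 and 5 are contradictions inside the charter.

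**2. Which text governs**

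- Towards the charter: charter Sections 2, 5 and 7; Section 7.3.2; Appendix B.
- Towards Appendix F: Sections 7.3.1 and 10.7.2.
- No sentence ranks one above the other.

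**3. The planned event count, as context**

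Inputs from Section 10.3: HR 0.65, two-sided alpha 0.05, power 80%, allocation 1:3, 279 events. With (1.960 + 0.842)² = 7.85:

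- Schoenfeld: 7.85 / (0.25 × 0.75 × (ln 0.65)²) = 226, which does not match 279.
- Freedman for unequal allocation, k = 1/3: 7.85 × (1 + 0.65/3)² / ((1/3) × 0.35²) = 284.5, about 2% above 279.

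The figure of 279 is not in dispute here.

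**4. Possible size**

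The documents give no share of events in rows 2 and 3. As an assumption, let 5%, 10% or 15% of 279 Appendix F events fall outside the charter definition, in equal proportion in both arms. Power is for fixed follow-up at HR 0.65, as Φ(√(d × c) − 1.96). Here c = (1/3) × 0.35² / (1 + 0.65/3)² = 0.0276 (Freedman), or 0.25 × 0.75 × (ln 0.65)² = 0.0348 (Schoenfeld).

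| Share | Events lost | Events counted | Power, Freedman | Power, Schoenfeld |
|---|---|---|---|---|
| 0% | 0 | 279 | 79% | 88% |
| 5% | 14 | 265 | 77% | 86% |
| 10% | 28 | 251 | 75% | 84% |
| 15% | 42 | 237 | 72% | 82% |

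If follow-up is extended to 279 counted events instead, power is kept and time is lost. Section 10.3 gives 1% per year in controls, and HR 0.65 implies 0.65% in the ILR group. The pooled rate is 0.75 × 1% + 0.25 × 0.65% = 0.9125%, or 6,000 × 0.009125 = 54.75 events a year, ignoring deaths and dropout. Replacing 14 events takes 14 / (54.75 × 0.95) = 0.27 years. Replacing 42 takes 42 / (54.75 × 0.85) = 0.90 years. That is roughly 3 to 11 months.

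**The case against.** A reader might infer that the charter removes haemorrhagic strokes, and so tilts the hazard ratio towards benefit, since screening leads to more anticoagulation. The documents do not support this. The charter lists haemorrhagic stroke as subtype 1b and asks for brain imaging to separate it from ischaemic stroke. Its bleeding section refers back to haemorrhagic stroke, and Appendix B has the committee class bleeds among strokes. Bleeds are plainly meant to count. What remains is a drafting fault: the infarction requirement contradicts the subtypes. A bias calculation would need a haemorrhagic share and a between-arm ratio, and the documents give neither.

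A reader might also infer that the endpoint being adjudicated is demonstrably not the one defined. That is too firm. It would follow if the charter governs, but Sections 7.3.1 and 10.7.2 point to Appendix F. The documents show an unsettled definition, not a substituted one.

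Three mitigating points carry weight:

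- **Blinding.** Adjudication is blinded and randomization details are obscured, so one wording applied to both arms does not by itself classify the arms differently.
- **Event-driven follow-up.** It can replace lost events, although Section 10.1 also allows the trial to end at 36 months.
- **Committee judgment.** The charter's note on TIA calls the 24-hour limit arbitrary, and Section 7 allows clinical judgment. Both may narrow the gap in practice.

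None of these supplies a charter category for a short deficit with infarction, brings global deficits into the charter, or says which text prevails.

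**Conclusion.** The point holds as an internal contradiction in the definition of the primary endpoint. The two texts classify short deficits with infarction on MRI, and global deficits, differently. The charter's general definition conflicts with its own haemorrhagic subtype, and the governing text is not stated.

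The number of events affected cannot be derived from the documents. On the assumed 5-15% it is about 14-42 of 279. That means roughly 3 to 11 months of extra follow-up at the planned rates or, with follow-up fixed, power of about 77-72% by the formula nearest the protocol's figure (86-82% by Schoenfeld). These sizes assume that the planning rates refer to Appendix F events and that both arms are affected in proportion. No direction of bias is shown.

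It should be corrected because the definition decides what counts towards the endpoint and towards the 279 events.

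**What to change.** 1. Replace the charter's stroke definition with the Appendix F text word for word, with subtypes 1a-1c. This brings in global deficits and the MRI criterion, and it removes the infarction requirement that conflicts with 1b. Appendix F is the natural source because Section 7.3.1 names it.
2. State in Section 10.7.2 and in the charter that Appendix F governs adjudication of the primary endpoint.
3. Have the existing committee re-check, blinded to allocation, any event already adjudicated under the charter wording that was under 24 hours with infarction on MRI, was a global deficit, or was haemorrhagic and not counted as stroke. Record how many classifications change.

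The cost is a charter amendment with a matching sentence in the protocol, and a short desk review. No new data collection or patient contact is needed.

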# ADJUDICATION OF SYSTEMIC EMBOLISMS (SYSTEMIC EMBOLIC EVENTS; SEE)

SEE include arterial embolic events except those that reach the brain; SEE may reach organs such as kidney, spleen, heart, intestine, eyes and extremities.

Adjudication is based on clinical evaluation of patient data.

#### ADJUDICATION OF BLEEDING EPISODES

Major bleeding is defined according to the ISTH criteria as bleeding in a critical site (e.g. symptomatic intracranial bleeding (hemorrhagic stroke (see above) or subdural hemorrhage)), or clinically overt bleeding accompanied by a decrease in the hemoglobin level of at least 20 g per deciliter or transfusion of at least 2 units of packed red cells, or bleeding resulting in death. Nonmajor bleeding is defined as clinically overt bleeding that does not satisfy the criteria for major bleeding but leads to hospital admission, physician-guided medical or surgical treatment, or a change in antithrombotic therapy.

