- Assessment of QoL and cognitive function: At randomization, months 12, 24 and 36.
- Vital signs (BP, HR ...): At randomization and at (12, 24), 36 months.
- 12-lead ECG: At randomization and at (12, 24), 36 months.
- Concomitant therapy: At randomization and months 12, 24, 36 and by lookup in medical records and registries at least on a yearly basis.
- Remote Loop Recorder readings: Daily
- Adverse events (AEs): At clinical visits and by lookup in medical records and registries at least on a yearly basis (see section 9 for definitions).

Information on all AEs, that occur from study day 1 after randomization will be recorded in the appropriate eCRFs on study visits and by lookup in medical records and registries at least on a yearly basis. All serious adverse events (SAEs) will be reported to the study office within one working day of discovery (see appendix C), and a SAE form must be completed (see section 9.3 for definitions). Bleeding complications will be registered according to the suggestions by the International Society for Thrombosis and Haemostasis (Schulman and Kearon, 2005). For the efficacy analysis of mortality, the endpoint committee (EC) will review all deaths and classify the events as cardiovascular or non-cardiovascular (see Appendix J). Cardiovascular deaths will be further classified as sudden and non-

sudden based on a time criteria (see Appendix J). Adjudicated cause of death as well investigatorreported cause of death will be entered into the eCRF.

A subgroup of those patients that underwent an echocardiography at inclusion will be invited to participate in a similar echocardiography during follow-up. The criteria for invitation is that the participants should have been included in the LOOP study before January 2017 at one of the study centres Rigshospitalet, Bispebjerg Hospital or Roskilde Hospital, and that the first echocardiography should be between 2 and 6 years old at the time of follow-up echocardiography.

For endpoints, see section 10.2

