# 10.2.3 Other Endpoints:

- Time to adjudicated intracranial hemorrhage not classified as stroke
- Time to major bleeding as defined by the International Society on Thrombosis and Haemostasis criteria
- Time to complications related to device implantation (Infection, hematoma, or other complication related to device implantation requiring intervention)

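### The Endpoint Committee Charter prints the haemoglobin criterion for major bleeding as a fall of 20 g per decilitre, probably a tenfold unit error, so one of the four routes to major bleeding cannot be met as written

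*Protocol*

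**What the plan says.** The definition is in the protocol's Appendix J (Endpoint Committee Charter), under Adjudication of bleeding episodes. It opens with "Major bleeding is defined according to the ISTH criteria as bleeding in a critical site". It then adds clinically overt bleeding with "a decrease in the hemoglobin level of at least 20 g per deciliter". Two further routes complete the sentence: "or transfusion of at least 2 units of packed red cells, or bleeding resulting in death". The routes are joined by *or*.

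The next sentence sets the lower category: "Nonmajor bleeding is defined as clinically overt bleeding that does not satisfy the criteria for major bleeding", provided that it led to admission, to treatment directed by a physician, or to a change in antithrombotic therapy.

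Two places in the body of the protocol refer to the same standard without printing a haemoglobin figure:

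- Section 10.2.3 lists "Time to major bleeding as defined by the International Society on Thrombosis and Haemostasis criteria".
- Section 7.2.1 says "Bleeding complications will be registered according to the suggestions by the International Society for Thrombosis and Haemostasis".

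The charter's figure is therefore the only numeric haemoglobin threshold in the protocol. Section 2 of the charter tells committee members to classify endpoints by the charter's own definitions.

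On what is adjudicated, section 10.2.3 also lists "Time to adjudicated intracranial hemorrhage not classified as stroke". Charter section 7, under "Events requiring adjudication include", names stroke or TIA, systemic embolism and death.

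**The concern.** A threshold that no patient can reach is a wrong decision rule in an endpoint definition. The haemoglobin route exists to catch serious bleeds that are outside a critical site, not fatal, and treated with fewer than 2 units. If the printed figure is followed, those bleeds fall to nonmajor. If they also led to no admission, treatment or change in therapy, they fall into no class.

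Bleeding matters in this trial because the screening strategy is meant to work by starting OAC. Section 1 names bleeding risk among the secondary objectives, section 2.4 undertakes to record harm as well as benefit, and section 12.1 says that bleeds may occur which participation itself brought about. A definition that drops some of these bleeds makes the absolute harm of screening look smaller than it is.

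There is also a risk of inconsistency. If some assessors silently correct the unit and others apply it as printed, like cases will be classed differently, in a trial where treatment is open-label.

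**Working it through.** **Inputs**

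- Printed threshold: a fall of 20 g/dL (Appendix J, bleeding definition).
- Remaining routes: critical site, at least 2 units transfused, death (same place).
- Baseline haemoglobin: the protocol gives no range. I assume 8 to 18 g/dL, which is deliberately wide.
- Expected OAC use: section 10.3 assumes that 30% have qualifying AF under monitoring, that 5% of the ILR group are not monitored, and that 3% of controls are diagnosed and start OAC.

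**Step 1. Can the printed criterion be met?**

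Unit conversion: 20 g/dL × 10 dL/L = 200 g/L.

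Level after the fall = baseline − threshold. The last column assumes that 20 g per litre (2 g/dL) was meant.

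| Baseline (g/dL) | After a fall of 20 g/dL | After a fall of 20 g/L (2 g/dL) |
|---|---|---|
| 8 | -12 | 6 |
| 10 | -10 | 8 |
| 12 | -8 | 10 |
| 14 | -6 | 12 |
| 16 | -4 | 14 |
| 18 | -2 | 16 |

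Every value in the middle column is impossible. Even a baseline of 20 g/dL would leave 0. Every value in the last column is possible, which is why a tenfold unit slip is the natural explanation. The intended figure cannot be confirmed from the protocol, because the ISTH number is not printed there.

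**Step 2. Which bleeds are affected?**

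| Type of overt bleed | Class under the printed text |
|---|---|
| Critical site (intracranial, for example) | Major, unaffected |
| Fatal | Major, unaffected |
| At least 2 units transfused | Major, unaffected |
| None of these, large haemoglobin fall | Nonmajor, or unclassified if there was no admission, treatment or change in therapy |

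Only the last row is lost.

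**Step 3. What happens to the comparison?**

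Let the true major-bleeding rates be λ₁ (ILR) and λ₀ (control). Let p₁ and p₀ be the shares that qualify through the haemoglobin fall alone.

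- Observed rates under literal use: (1 − p₁)λ₁ and (1 − p₀)λ₀.
- Observed ratio: (λ₁/λ₀) × (1 − p₁)/(1 − p₀).
- If p₁ = p₀ = p, the ratio is unchanged, and the difference becomes (1 − p)(λ₁ − λ₀).

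With equal shares, the relative effect is preserved, the absolute excess shrinks by the fraction p, and there are fewer events, so precision falls. The ratio is distorted only if the shares differ between arms, and the protocol says nothing about that.

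The design expects much more OAC in the ILR arm: 30% × 95% = 28.5% if all who qualify accept it, against 3% of controls. An absolute excess of bleeding in that arm is therefore what one would look for, and it is the quantity that would be understated.

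**Step 4. Size of p.** No share of bleeds by qualifying route and no bleeding rate is given anywhere in the protocol, so p cannot be estimated.

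**The case against.** The strongest reply is that the printed number is a faulty paraphrase of a named standard. Sections 7.2.1 and 10.2.3 and the charter itself all refer to the ISTH criteria. The assessors are a neurologist and a cardiologist, who would be likely to recognise an impossible figure. It is also unclear whether the charter decides this endpoint at all. Its section 1 speaks of adjudicating the primary endpoints, its section 7 list omits bleeding, and section 10.2.3 attaches the word adjudicated to non-stroke intracranial haemorrhage but not to major bleeding.

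This stands to the extent that literal use is a possibility, not something the protocol shows. It does not remove the error. The charter offers its text as the ISTH definition, prints the only threshold, and tells members to use its definitions.

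A reader might infer several stronger things that the documents do not support:

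- *That major bleeding as a whole cannot be met.* The fall is one of four alternatives. Fatal and critical-site bleeds, and those with at least 2 units transfused, still count.
- *That this is the main safety endpoint.* Section 10.2.3 places major bleeding among the other endpoints, the synopsis among the secondary ones, and section 10.6.2.3 on safety does not name it.
- *That the hazard ratio is tilted towards screening.* Step 3 shows that this needs unequal shares in the two arms, and nothing in the protocol indicates them.
- *That a definite number of events is lost.* Any count would rest on an assumed share and an assumed bleeding rate.

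The mismatch over intracranial haemorrhage is a separate and weaker matter. The section 7 list is worded so that it need not be exhaustive. Charter section 1 takes in trial endpoints and important adverse events, and a later charter heading covers bleeding and names subdural haemorrhage. Adjudication of this endpoint is poorly signposted rather than absent.

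**Conclusion.** The printed haemoglobin criterion is wrong as written. A fall of 200 g/L exceeds the total haemoglobin of any realistic patient, and this conclusion holds over the whole assumed baseline range of 8 to 18 g/dL. It is probably a unit error.

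If applied literally, it disables one of four routes and removes from major bleeding the overt, non-critical-site, non-fatal bleeds with a large haemoglobin fall and fewer than 2 units transfused. Counts would be lower, and the absolute excess in the arm with more OAC would be understated by the share of bleeds that qualify through that route alone. That share is unknown. The relative effect need not be biased. Whether any bleed has been misclassified depends on whether assessors used the charter's figure or went to ISTH directly, and the protocol cannot settle that.

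The point concerns a non-primary endpoint, but the correction is due because the figure is a decision threshold and nothing else in the document overrides it with a number.

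**What to change.** 1. Correct the unit in the charter's bleeding definition after checking the ISTH source that sections 7.2.1 and 10.2.3 rely on. The presumed intention is 20 g per litre (2 g per decilitre), to be confirmed at source before it is printed.
2. Establish which definition was used for bleeds already recorded. Re-classify any that were judged by the printed figure, without knowledge of treatment group. If none were, say so in a note to file.
3. As a tidy-up, add non-stroke intracranial haemorrhage to the list in charter section 7 so that it agrees with section 10.2.3. State in the same place whether major bleeding is adjudicated by the committee or classified by the sites.

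The cost is a short charter correction, a desk review of recorded bleeds, and possibly a few more cases for the existing committee. Sample size, visits and the primary analysis are untouched.
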